
Study Products
	
Methylprednisolone succinate and prednisone (Corticosteroids, CS) Dapagliflozin (Sodium-glucose cotransporter 2 inhibitor, SGLT2i)

Treatments
	
ACiGaN Study
 
IgAN Active renal lesions
 
Experimental arm: Corticosteroids + RASBs (4 months) → RASBs (4 months) → RASBs (28 months)
 
Control arm (KDIGO): RASBs (4 months) → RASBs + Corticosteroids (4 months) → RASBs (28 months)
 <hr/> 
CHRONiGaN Study
 
IgAN Chronic renal lesions Moderate renal lesions
 
Experimental arm: RASBs (4 months) → RASBs + Dapagliflozin (6 months) → RASBs + Dapa (26 months)
 
Control arm (KDIGO): Run-in → RASBs + Corticosteroids (6 months) → RASBs (26 months)
 
Patients will be randomized separately in each trial (allocation 1 to 1 ratio). Stratified randomization will be done by age and sex in renal centers.
 
ACiGaN trial
 
Experimental arm: Early corticosteroids therapy combined with RASBs followed by RASBs treatment.
 
Control arm (standard care): RASBs treatment followed by corticosteroids combined with RASBs and then only RASBs.
 
CHRONiGaN trial
 
Experimental arm: RASBs therapy followed by Dapagliflozin combined with RASBs.
 
Control arm (standard care): RASBs therapy followed by Corticosteroids combined with RASBs and then RASBs alone

Sample Size and Statistics
	
ACiGaN. Data from the literature have shown a difference in renal survival between corticosteroids and controls when the researchers assumed a difference of 50% in the primary end point (i.e., in the between-arms difference of delta 24 hour proteinuria from base-line to 6 months) as clinically relevant. Therefore, we assume that a mean delta proteinuria from base-line to 6 months in patients treated with RASBs alone (control arm) is 0.6 ± 1.0 g/24 hours (\pmSD) versus a mean delta proteinuria 1.2 ± 1.0 g/24 hours (\pmSD) from base-line to 6 months in patients treated with RASBs and corticosteroids (experimental arm). Based on these assumptions, we calculated a sample size of 132 patients (66 patients per group including a 10% dropout rate) for a power of 90%, a two-sided significance level of 0.05 and 3 years

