1.2. Rationale

In our CLlIgAN study, we have planned to evaluate:

- (i) The effect of early start corticosteroid therapy combined with RASBs (experimental arm) versus RASBs alone in IgAN patients with active renal lesions (AClIgAN) who will receive corticosteroids after 4 months of RASBs (standard care) in presence of persistent proteinuria ≥ 0.5 g/24 hours and eGFR ≥ 30 ml/min/1.73 m² (control arm).
- (ii) The effect of SGLT2i (dapagliflozin) combined with RASBs (experimental arm) versus corticosteroids combined with RASBs (control arm) in IgAN patients with chronic or moderate renal lesions (CHRONlIgAN) after a run-in phase of 4 months in which they will receive RASB therapy alone (standard care).

In both studies patients enrolled in the control arms will be treated according to the evidence-based recommendations (standard care) provided within the KDIGO guidelines.

In conclusion, we would like to evaluate the effect of early start corticosteroids in IgAN patients with active renal lesions (AClIgAN) and to spare corticosteroids therapy in IgAN with chronic or moderate renal lesions (CHRONlIgAN) administering Dapagliflozin.

We would also provide earlier ESKD risk prediction by using our tool DialCheck (32).

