3. TRIAL DESIGN

This project encompasses two prospective, multicentre, open-label randomized controlled clinical trials (RCTs) of IgAN patients (CLlGaN) based on the kidney biopsy report (*Figure 1*).

Stratified randomization will be done by age and sex in renal centers.

[figure not shown]

Figure 1

ACiGaN TRIAL

Patients with active renal lesions (E1 and/or C1) in the presence of $GFR \geq 30$ ml/min/1.73 m² and proteinuria ≥ 0.5 g/24 hours will be randomized into two arms:

- 1) corticosteroids combined with RASBs for 4 months followed by RASBs alone (experimental arm);
- 2) RASBs alone for 4 months followed by the combination corticosteroids and RASBs for 4 additional months and then only RASBs (standard care) as suggested by KDIGO guidelines (5).

Participants assigned to the experimental arm will receive by 2 weeks from the kidney biopsy (pulse) methylprednisolone (SOLU-Medrol) 500-1000 mg in the first day and then 50% of dose in the next two days followed by oral prednisone (0.5 mg/kg/bw) on alternate days until the end of the month. This treatment will be repeated for three consecutive months. After three months, participants will gradually reduce oral prednisone, in the course of four weeks. Next, they will receive RASBs alone.

The daily dose of methylprednisolone will be individualized (15 mg/kg), based on the ideal body weight. The drug will be administered in a single dose intravenously for 30-60 min. To avoid obesity and diabetes corticosteroids will be administered only in the morning.

This is a parallel group, two arm, superiority trial with 1:1 allocation ratio.

As per standard care RASB therapy will be titrated to its maximum labelled or tolerated dose as anti-proteinuric effect in every patient.

Rationale of the study design

Corticosteroids at high dosage have been administered in RCTs of IgAN (18,41) independent of the type of renal lesions despite empiric evidence from clinical practice and strong and consistent evidence from observational studies that the lesions identified at kidney biopsy may play a role in the response to treatment. Our aim is to evaluate the benefit of early pulse therapy combined with oral prednisone only in IgAN patients with active renal lesions. In our protocol, we have excluded intensive immunosuppressive therapy (CS+CYP/AZA/MMF) because RCTs have demonstrated that the potential benefits-harms trade off is in favour of the harms (42).

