4.4 Outcome measures

The primary endpoint is the 24 h-proteinuria reduction between arms as suggested by Inker LA et al (44). It will be assessed after 4 and 8 months in the ACiGaN study and after 10 months in the CHRONiGaN trial.

The secondary end point is the GFR slope calculated as the mean of individual slope obtained from individual linear regression of eGFR overtime (3 years). Based on the International Consensus definition of clinical trial outcomes for kidney failure (23) we have also considered other secondary end points listed below.

Primary and secondary end points that will be evaluated in the two RCTs are listed below:

Primary endpoint:

- Between-arms difference in proteinuria reduction within 4 and 8 months in ACiGaN and within 10 months in CHRONiGaN study.

Secondary endpoints:

- eGFR slope calculated as mean of individual slope obtained from individual linear regression of eGFR overtime (3 years);
- eGFR decline > 40 % from the baseline value;
- composite end point: GFR decline > 40%, ESKD (defined as long-term GFR \leq 15 ml/min/1.73m² for more than three months or need for maintenance dialysis or kidney transplantation) or death due to kidney disease;
- absolute difference between last GFR value and baseline GFR;
- stable renal function defined as a decline in GFR \leq 5 ml/min/1.73m² at the end of three years follow-up;
- mean annual change in the slope of the reciprocal of serum creatinine concentration;
- time-averaged proteinuria (TA-P) calculated as the weighted mean of all post-randomization measurement, with weights representing the time elapsed since the previous measurement;
- proteinuria slope, calculated as a mean of individual slope, obtained from individual linear regression of daily proteinuria overtime (3 years);
- complete remission of proteinuria defined as achievement of urinary protein level \leq 0.2 g/day or a urinary protein-to-creatinine ratio \leq 0.2 g/g;
- partial remission of proteinuria defined as achievement of a urinary protein reduction \geq 50% or greater compared with baseline value.

The end points will be evaluated monthly in IgAN patients with active renal lesions in the first eight months after kidney biopsy and then every three months. In IgAN patients with chronic or moderate renal lesions the end points will be evaluated every three months in the first two years after the enrollment and then every six months.

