6. SAMPLE SIZE AND STATISTICAL METHODS

ACIGAN. Data from the literature (22,23) have shown a difference in renal survival between corticosteroids and controls when the researchers assumed a difference of 50% in the primary end point (i.e. in the between-arms difference of delta 24 hour proteinuria from baseline to 6 months) as clinically relevant. Therefore, we assume that a mean delta proteinuria from baseline to 6 months in patients treated with RASBs alone (control arm) is 0.6 ± 1.0 g/24 hours (\pm SD) versus a mean delta proteinuria that is 1.2 ± 1.0 g/24 hours (\pm SD) from baseline to 6 months in patients treated with RASBs and corticosteroids (experimental arm). Based on these assumptions, we calculated a sample size of

132 patients (66 patients per group including a 10% dropout rate) for a power of 90%, a two-sided significance level of 0.05 and 3 years of recruitment. If the number of the enrolled patients will be insufficient, the recruitment period will be extended for two years.

CHRONiGaN. Data from the literature (29-31) have shown a difference of renal survival between SGLT2is and controls. There are no data in the literature exploring the difference of renal survival or proteinuria between SGLT2is and steroids. Here, the researchers assumed an opportunistic sample of 300 patients for this first comparative study (150 patients per group, including a 10% dropout rate).

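### In ACiGaN, a single straight-line proteinuria slope over 3 years counts an early advantage against the early-steroid arm and can rank delayed steroids first if the control arm catches up

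*Protocol*

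**What the plan says.** Protocol section 4.4 defines the secondary endpoint as "proteinuria slope, calculated as a mean of individual slope, obtained from individual linear regression of daily proteinuria overtime (3 years"). One line is fitted per patient. There is no split into phases, and the text does not say whether the baseline value enters the fit. The same list contains "time-averaged proteinuria (TA-P) calculated as the weighted mean of all post-randomization measurement", weighted by the time since the previous measurement.

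Section 3 gives the ACiGaN experimental arm "corticosteroids combined with RASBs for 4 months followed by RASBs alone (experimental arm") and the control arm "RASBs alone for 4 months followed by the combination corticosteroids and RASBs for 4 additional months". The Synopsis shows the control sequence as "RASBs (4 months) → RASBs + Corticosteroids (4 months) → RASBs (28 months"). Section 1.2 makes the control-arm course conditional: these are patients "who will receive corticosteroids after 4 months of RASBs (standard care) in presence of persistent proteinuria" of at least 0.5 g/24 h with adequate eGFR.

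Section 1.5 counts a reduced proteinuria slope among the drug benefits. I read that as a more negative slope being better. For eGFR, section 6.1 plans acute, chronic and total slopes; for proteinuria it names only one slope.

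**The concern.** The treatment schedules differ only in the first 8 months; after that both arms are on RASBs. If proteinuria falls under treatment and then levels off, a straight line through all 36 months is steeper when the fall comes later. The arm that improves first then gets the less negative slope, which this endpoint reads as the smaller reduction.

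A listed efficacy endpoint could thus report early steroids as inferior while early-arm proteinuria is equal or lower at every visit, contradicting TA-P in the same table of results.

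**Working it through.** **Plan's own figure.** Section 6 assumes a "mean delta proteinuria from baseline to 6 months in patients treated with RASBs alone (control arm) is 0.6" g/24 h, against a "mean delta proteinuria that is 1.2" g/24 h with steroids, SD 1.0 in each arm. At 90% power and two-sided 0.05, n = 2 x (1.960 + 1.282)² x 1.0² / 0.6² = 58.4, so 59 per arm; 59 / 0.9 = 65.6, so 66 per arm and 132 in all. The stated size reproduces and is not in question. The two falls are reused below.

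**Inputs.** Visits from Figure 2A: baseline (taken as month 0) and months 1, 2, 4, 6, 8, 12, then every 3 months to 36. Falls of 0.6 and 1.2 g/24 h from section 6.

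My assumptions, not in the protocol:
- linear falls over 4 months, flat curves afterwards, complete visits
- the 6-month falls applied at month 4 (and at month 8 for the control arm's second step)
- a start of 2.0 g/24 h; between-arm differences do not depend on it

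Early arm: 2.0 to 0.8 by month 4, then flat. Control arm: 2.0 to 1.4 by month 4, then a further 0.6 x r by month 8, then flat. Here r is the share of the extra 0.6 g recovered after late steroids. Early is lower or equal at every visit for every r from 0 to 1.

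**Formula.** With complete visits the mean of individual slopes equals the slope of the mean curve. The early-minus-control slope difference is 12 x sum[(t - mean t) x g(t)] / sum[(t - mean t)²] g/day per year, where g(t) is the early-minus-control gap at visit t. With baseline, mean t = 237/15 = 15.8 months and the denominator is 2100.4. Without baseline they are 237/14 = 16.9 months and 1832.9. Months 1 to 8 all lie before the mean, so a negative gap there contributes positively.

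**Full catch-up (r = 1), baseline included.** Gaps are -0.15, -0.30, -0.60 and -0.30 at months 1, 2, 4 and 6, and zero from month 8. The sum is (-14.8)(-0.15) + (-13.8)(-0.30) + (-11.8)(-0.60) + (-9.8)(-0.30) = 2.22 + 4.14 + 7.08 + 2.94 = 16.38. The difference is 12 x 16.38 / 2100.4 = +0.094. The slopes themselves are -0.232 (early) and -0.325 (control).

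**No late steroid effect (r = 0), baseline included.** The gap stays at -0.60 from month 4 and the sum is -20.28. The difference is 12 x (-20.28) / 2100.4 = -0.116.

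**TA-P.** Early: (1.7 + 1.4 + 0.8 x 34) / 36 = 0.842. Control, r = 1: (1.85 + 1.7 + 2.8 + 2.2 + 1.6 + 0.8 x 28) / 36 = 0.904. Control, r = 0: (1.85 + 1.7 + 1.4 x 34) / 36 = 1.421.

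Differences, early minus control (negative favours early):

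| Share recovered, r | Slope, with baseline | Slope, without baseline | TA-P, g/day |
|---|---|---|---|
| 0 | -0.116 | -0.076 | -0.58 |
| 0.50 | -0.011 | +0.020 | -0.32 |
| 0.55 | -0.001 | +0.030 | -0.30 |
| 0.75 | +0.041 | +0.069 | -0.19 |
| 1 | +0.094 | +0.117 | -0.06 |

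**Where the sign turns.** The difference is linear in r. With baseline, r = 0.116 / (0.116 + 0.094) = 0.55; without, r = 0.076 / (0.076 + 0.117) = 0.39. With baseline, the slope therefore shows a tie when early still holds a lasting advantage of 0.6 x (1 - 0.553) = 0.27 g/day.

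**Sensitivity.** Section 4.4 describes monthly evaluation to month 8 and three-monthly evaluation after that. On two readings of that schedule, with and without baseline, full catch-up gives +0.114 to +0.136, no late effect gives -0.060 to -0.095, and the sign turns at 31% to 45% recovery. Letting the falls run to month 6 instead gives +0.085 to +0.127 for full catch-up over all schedules.

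**The case against.** A reader might infer that the slope always puts delayed steroids first, or is biased against early treatment by construction. The documents do not support that. Section 1.1 argues that lesions become chronic within 3-6 months and that steroids may then do nothing. On that hypothesis the control arm stays near its RASB-only level and the slope correctly favours early treatment (-0.116, or -0.076 without baseline). A gap that widens during follow-up also favours early (about -0.18 to -0.22). Full catch-up is the extreme case, and conditional control-arm steroids under section 1.2 lower the average catch-up. All of this stands and limits the point to a conditional one.

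It is also true that this is one secondary endpoint of ten. The primary endpoint, TA-P, the remission endpoints and the repeated-measures models in section 6.4 all address proteinuria. They limit the harm but do not correct this endpoint.

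The defence does not rescue the slope itself. Whether late steroids still work is what the trial sets out to learn, and the sign of this endpoint depends on the answer. At 50% recovery it even depends on the unstated baseline rule, while TA-P favours early by 0.32 g/day. Nor is this detail left to an analysis plan: the protocol itself fixes a single regression over 3 years.

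**Conclusion.** The point holds in conditional form. The 3-year single-line slope gives negative weight to an advantage in months 1-8, whatever the curves look like later. On Figure 2A visits it ranks delayed above early steroids, with early never worse at any visit, once the control arm recovers more than about 55% (baseline in the fit) or 40% (baseline excluded) of the extra 0.6 g/24 h. Over the full range of recovery the slope difference changes sign, whereas TA-P keeps the same ranking.

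The sign of the early weight is algebra. The sizes rest on the assumed linear falls, flat plateaus, timing of the section 6 falls and complete visits; the protocol gives no proteinuria assumption beyond month 6. The finding concerns ACiGaN only.

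**What to change.** In section 4.4, state that for ACiGaN the 3-year single-line proteinuria slope is not a between-arm efficacy endpoint, and that TA-P carries that question. If a slope is kept, fit it from month 8, when both scheduled steroid courses have ended, and label it durability of response, not treatment effect.

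The cost is one listed secondary endpoint dropped or relabelled. A slope from month 8 leaves out the months of the planned contrast, which is why it must not be read as the treatment effect. No new visits or data are needed.

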To our knowledge, this is the first study in which corticosteroids are administered immediately after the kidney biopsy in IgAN patients with active renal lesions. Based on the existing evidence from randomized clinical trials, the KDIGO guidelines suggest in those cases: RASBs for 3-6 months and then corticosteroids in presence of persistent proteinuria and $GFR >30$ ml/min/1.73 m². This therapeutic approach, although supported by evidence, may be a challenge based on empiric clinical knowledge supported also by findings of cohort studies. This demonstrates that after 3-6 months active renal lesions become chronic and consequently no association may be found between exposure to corticosteroids and clinical response for IgAN patients. In our randomized clinical study we compare the standard approach proposed by KDIGO guidelines (RASBs for 3-6 months followed by corticosteroids) vs a novel approach consisting of early corticosteroid therapy combined with RASBs from the beginning.

CHRONIgAN TRIAL

Patients with chronic (T1,2) or moderate renal lesions (M0,1; S0,1, E0, C0, T0) will be enrolled in a two-arm trial with 1:1 allocation ratio to compare Dapagliflozin combined with RASBs (experimental arm) versus corticosteroids combined with RASBs (control arm) after 4 run-in months of RASBs treatment. The enrolled patients will have proteinuria ≥ 0.5 g/day and GFR ≥ 30 ml/min/1.73 m².

Participants will receive study treatments by 4 weeks from the kidney biopsy.

Patients assigned to the experimental arm will receive RASBs therapy (4 run-in months) followed by Dapagliflozin (10 mg /day orally) combined with RASBs for a total of 32 consecutive months. Patients assigned to the control arm will receive RASBs therapy (4 run-in months) followed by oral corticosteroids therapy (prednisone) for six months (0.4 mg/kg body weight for 2 months and then gradual reduction of 5 mg/day for 4 months) and then RASBs alone for a total of 36 consecutive months.

This is a parallel group, two arm, superiority trial with 1:1 allocation ratio.

Rationale of the study design

We decided the combination Dapagliflozin and RASBs because recently, SGLT2is were administered in patients with type 2 diabetes and in other participants with CKD (some of them were affected by IgAN) (29-31). In these studies, the effect of SGLT2is was compared with a placebo.

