4.5 Participant timeline

Total Study duration: approximately 6 years:

- Enrollment period: 3 years
- Treatment and Follow-up period: 3 years + 30 days.

Figure 2A and **2B** illustrate the time schedule of enrollment, interventions, assessments and visits for participants.

Figure 2A. SPIRIT 2013 STATEMENT OF THE ACiGAN STUDY: Time schedule of the enrolment, interventions, assessments and visits of the participants.

Time point	STUDY PERIOD																			
	Enrolment	Allocation	Post-allocation														End of Treatment	End of Study		
			t ₁	t ₂	t ₄	t ₆	t ₈	t ₁₂	t ₁₅	t ₁₈	t ₂₁	t ₂₄	t ₂₇	t ₃₀	t ₃₃	t ₃₆				
	- t ₁	t ₀															t ₃₆	30 days after last treatment		
Enrolment:																				
Eligibility screen	x																			
Informed consent	x																			
Kidney biopsy	x																			
Laboratory data	x																			
Allocation		x																		
Interventions:																				
(A) Cs+RASBs (4 months) → RASBs			●	—————														●		
(B) RASBs (4 months) →Cs+RASBs (4 months)→RASBs			●	—————														●		
Assessments:																				
Serum creatinine	x		x	x	x	x	x	x	x	x	x	x	x	x	x	x	x			
eGFR	x		x	x	x	x	x	x	x	x	x	x	x	x	x	x	x			
Daily proteinuria	x		x	x	x	x	x	x	x	x	x	x	x	x	x	x	x			
Adverse events	x		x	x	x	x	x	x	x	x	x	x	x	x	x	x	x		x	
Concomitant medications	x		x	x	x	x	x	x	x	x	x	x	x	x	x	x	x		x	
Outcome variables:																				
Proteinuria reduction (primary end point)						x	x	x	x	x	x	x	x	x	x	x	x	x		
eGFR slope reduction (secondary end point)			x	x	x	x	x	x	x	x	x	x	x	x	x	x	x	x		
Biological samples collection		x	x	x	x	x	x	x				x				x				

Figure 2B. SPIRIT 2013 STATEMENT OF THE CHRONIGAN STUDY: Time Schedule of the enrolment interventions, assessments and visits of the participants.

Time point	STUDY PERIOD															
	Enrolment	Allocation	Post-allocation												End of Treatment	End of Study
	- t ₁	t ₀	t ₁	t ₄	t ₈	t ₁₀	t ₁₂	t ₁₄	t ₁₈	t ₂₄	t ₂₇	t ₃₀	t ₃₃	t ₃₆	t ₃₆	30 days after last treatment
Enrolment:																
Eligibility screen	x															
Informed consent	x															
Kidney biopsy	x															
Laboratory data	x															
Allocation		x														
Interventions:																
(A) RASBs (4 months)→ Dapagliflozin +RASBs			●	—————											●	
(B) RASBs (4 months)→ Cs+RASBs(6 months)→RASBs			●	—————											●	
Assessments:																
Serum creatinine	x		x	x	x	x	x	x	x	x	x	x	x	x		
eGFR	x		x	x	x	x	x	x	x	x	x	x	x	x		
Daily proteinuria	x		x	x	x	x	x	x	x	x	x	x	x	x		

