6.1 Recruitment

Rationale: In some RCTs (22,23) IgAN patients received three - six months of RASBs treatment before their enrollment for corticosteroid therapy. In our opinion this approach is not correct because the active renal lesions evolve in the chronic stage and are no-responsive to corticosteroid therapy. Therefore, the aim of our RCT is early treatment of the active renal lesions because they are responsible for altered GFR and proteinuria.

Recruitment: IgAN patients will be enrolled within 2-4 weeks from the kidney biopsy in renal centers. The kidney biopsy will be scored according to the Oxford classification (6-8) because it is a simple method for predicting renal outcomes and for scoring active and chronic renal lesions (46). Therefore, the kidney biopsy will be the principal key-note, not only for diagnosis but also for personalized therapy, because active renal lesions (E1,C1) will be treated with immediate corticosteroid therapy before lesions become chronic.

The kidney biopsy will be analyzed using digital histopathologic analysis coupled with machine-learning tools. At least eight glomeruli will be available for a correct diagnosis. Immunofluorescence technique will be used to determine the relevance of mesangial IgA deposits in the glomeruli. Renal tissue sections will be stained with hematoxylin and eosin, periodic acid-Schiff and methenamine silver. The last edition of the Oxford classification (MESTC) (8) will be used for the scoring of the renal lesions. Active renal lesions are endocapillary (E) and extracapillary (C) proliferative lesions while T lesions (T1,2) are expression of chronic renal lesions and severe outcome (46-49). Other histological lesions will be evaluated as fibrinoid necrosis, global glomerulosclerosis and arteriolosclerosis.

Three independent renal pathologists, blinded to the study results, will score the lesions in the kidney biopsy using the Aperio System. The histology report will be necessary for the enrollment of patients. No larger RCT has confirmed that the disease improves when clinical decisions are made in a short time in the presence of the MESTC score.

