6.2 Allocation

After initial eligibility based on screening of the clinical data and kidney biopsy report, each patient will receive an explanation of the trial plan. After the signature of the consensus participation the patient will be enrolled and randomized separately in each trial (allocation 1 to 1 ratio) via a web-based program generating random numbers to ensure allocation concealment. Stratified randomization will be done by age and sex in renal centers. The follow-up study to measure the outcomes will consist of regular visits at the prescribed times to collect clinical and laboratory data and information on drug adherence. Before the trial is complete, each patient will receive a final outpatient visit.

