9.5 Collection of biological samples

In this project we will collect blood, kidney biopsy and urine samples from IgAN patients with acute renal lesions enrolled in the ACIgAN clinical study and from IgAN patients with chronic and moderate renal lesions enrolled in the CHRONIgAN trial. Blood and urine samples will be collected

in every patient on the same day before kidney biopsy will be performed and then during the clinical course of the disease. IgAN patients will be accurately stratified by the MEST-C classifications.

Blood and urine samples will be collected at different time (T) from patients during the follow-up of the CLlIgAN study:

- i) patients with active renal lesions: T0,T1,T2,T4,T6, T8,T12,T24, T36 months and
- ii) in patients with chronic and moderate renal lesions: T0,T1,T4,T8,T10,T14,T24,T36 months.

Blood samples. 10 ml of blood will be collected in PAXgene tubes for the isolation of peripheral blood leukocytes that will be used for transcriptomic studies.

Serum samples will be collected for the measurement of IgA, Gd-IgA1 and other biomarkers. Some of these biomarkers have been described as predictors of clinical outcome but none has been validated in prospective clinical studies. Therefore, we will measure some current biomarkers involved in the pathogenesis of the disease as Gd-IgA1 during the follow-up.

Urine samples. 30-50 ml of urine of the second morning urination will be collected for the isolation of urinary microvesicles.

Renal biopsy will be used for histological diagnosis and immunofluorescent technique. Then, transcriptomics will be performed in RNA eluted from 5 micron thickness sections for a total of 8 slides.

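### The visit-frequency sentences closing Section 4.4 contradict that section's own month-10 CHRONiGaN primary endpoint and the visit schedules in Figures 2A and 2B

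*Protocol*

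**What the plan says.** Section 4.4 of the protocol says of the primary endpoint, 24-hour proteinuria reduction: "It will be assessed after 4 and 8 months in the ACiGaN study and after 10 months in the CHRONiGaN trial". Its last paragraph then sets how often endpoints are evaluated. For ACiGaN: "The end points will be evaluated monthly in IgAN patients with active renal lesions in the first eight months after kidney biopsy", and three-monthly after that. For patients with chronic or moderate lesions: "the end points will be evaluated every three months in the first two years after the enrollment and then every six months".

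Section 4.5 introduces Figures 2A and 2B, which "illustrate the time schedule of enrollment, interventions, assessments and visits for participants". Both mark daily proteinuria, serum creatinine and eGFR at every post-allocation visit:

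- Figure 2A (ACiGaN): months 1, 2, 4, 6, 8, 12, 15, 18, 21, 24, 27, 30, 33, 36.
- Figure 2B (CHRONiGaN): months 1, 4, 8, 10, 12, 14, 18, 24, 27, 30, 33, 36.

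Section 9.5 lists CHRONiGaN sampling at "T0,T1,T4,T8,T10,T14,T24,T36 months". Section 3 compares the CHRONiGaN arms "after 4 run-in months of RASBs treatment", so dapagliflozin or prednisone starts at month 4 and the six-month prednisone course runs to month 10. Section 6.4 gives different time points for the primary comparison: baseline to 6 months in ACiGaN and baseline to 12 months in CHRONiGaN. No order of precedence between text and figures is stated.

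**The concern.** Section 4.4 fixes a primary assessment month and then states an evaluation frequency that skips it. A site that plans its CHRONiGaN visits from the frequency sentence would collect 24-hour urine at months 9 and 12, not at month 10. Those are not interchangeable substitutes. At month 9 the control arm is still within its prednisone course. At month 12 it has been off prednisone for two months while the other arm continues dapagliflozin. The treatment contrast therefore differs between the two visits, and an analysis plan cannot recover a urine collection that was never made.

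The secondary endpoints depend on the grid too. Time-averaged proteinuria weights each value by the time since the previous one, and the eGFR and proteinuria slopes are individual regressions over all visits. If the more than 30 sites divided between two grids, the number and spacing of values per patient would vary by site.

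**Working it through.** The plan states no figure to reproduce here. The check expands each rule into months and compares it with the figure.

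**CHRONiGaN, counted from enrolment at about allocation**

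- Text rule: 3, 6, 9, 12, 15, 18, 21, 24 (every three months for two years), then 30, 36. Total 8 + 2 = 10 visits.
- Figure 2B: 8 visits to month 24 (1, 4, 8, 10, 12, 14, 18, 24), then 27, 30, 33, 36. Total 8 + 4 = 12 visits.
- In both: 12, 18, 24, 30, 36 (5 visits).
- Only in the text: 3, 6, 9, 15, 21. Only in the figure: 1, 4, 8, 10, 14, 27, 33.
- Month 10: the adjacent text visits are month 9 (10 − 9 = 1 month early) and month 12 (12 − 10 = 2 months late).
- Month 4: the adjacent text visits are month 3 (1 month early) and month 6 (2 months late).
- Section 9.5 sampling after T0 (1, 4, 8, 10, 14, 24, 36): all seven months are in Figure 2B; only 24 and 36 are in the text rule.

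**Does the starting point of the count matter?** If enrolment preceded t0 by s months, each text visit falls at (visit − s) on the figure's clock.

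| s (months) | First visits on the figure's clock | Month 4 met | Month 10 met |
|---|---|---|---|
| 0 | 3, 6, 9, 12 | no | no |
| 0.5 | 2.5, 5.5, 8.5, 11.5 | no | no |
| 1 | 2, 5, 8, 11 | no | no |
| 2 | 1, 4, 7, 10 | yes | yes |

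A two-month gap does not fit the document. Section 6.1 says "IgAN patients will be enrolled within 2-4 weeks from the kidney biopsy in renal centers", Section 3 has study treatment begin by 4 weeks from biopsy, and Section 6.2 says that after consent "the patient will be enrolled and randomized separately in each trial". If enrolment meant the end of the run-in, the six-month visit would fall at 4 + 6 = month 10. But Sections 6.1 and 6.2 and Figure 2B all put enrolment and allocation before the four months of RASBs.

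**ACiGaN, two ways of counting the three-monthly visits**

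- Restarting at month 8: 1 to 8, then 11, 14, 17, 20, 23, 26, 29, 32, 35 (8 + 9 = 17 visits). Shared with Figure 2A: 1, 2, 4, 6, 8; none later.
- Calendar multiples of three: 1 to 8, then 9, 12, 15, ..., 36 (8 + 10 = 18 visits). All 14 Figure 2A visits are included; the text adds only 3, 5, 7 and 9.
- On either count months 3, 5 and 7 are in the text and not in the figure, and months 4 and 8 are in both.
- The text counts from kidney biopsy and the figure from allocation, so nominally equal months can differ by the gap between the two.

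**Time points in Section 6.4.** Month 6 is in Figure 2A and in both ACiGaN counts. Month 12 is in Figure 2B and in the CHRONiGaN text rule.

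**The case against.** The strongest reply is that the protocol does call for month 10. Section 4.4 says so when it defines the endpoint, Figure 2B marks proteinuria at months 4 and 10, Section 9.5 samples at both, and the 10-month point recurs in Sections 4.4.1 and 6.5. Section 4.5 is the part that sets visits, so the closing sentences of Section 4.4 can be taken as a loose description of frequency. This stands as a limit on the consequence. A reader might infer that CHRONiGaN has no primary-endpoint measurement at all; the documents do not support that. It does not remove the contradiction, because the sentence is worded as a schedule, sits in the same section as the endpoint, and nothing says the figure prevails.

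Two other strong readings also fail. A reader might infer that without month 4 there is no value from before the arms diverge. Both arms take RASBs alone until month 4, so the enrolment value and the text's month-3 visit both precede divergence. A reader might also infer that the two ACiGaN schedules never meet after month 8. That holds only if the three-month count restarts at month 8, a series that ends at 35 and never reaches month 36; on calendar quarters every Figure 2A visit is in the text.

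Finally, the month-10 endpoint is itself unsettled, since Section 6.4 names month 12, which both CHRONiGaN grids contain. That is a fair point, and it means that correcting the visit sentences alone would leave the protocol contradictory.

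**Conclusion.** The point holds as an internal inconsistency, not as a criticism of a design choice. The CHRONiGaN frequency sentence omits the primary month given in the same section and the month when the add-on drug starts, and agrees with Figure 2B at 5 of the figure's 12 visits. This assumes that enrolment is at or within about a month before allocation, as Sections 6.1 and 6.2 and Figure 2B indicate, and that month 10 is the intended primary time point. How many month-10 values would be lost cannot be derived: it depends on how many sites follow the sentence and not the figure, and the document gives no basis for estimating that.

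For ACiGaN the conflict is milder. No primary time point named in Section 4.4 is lost. The text asks for months 3, 5 and 7, possibly 9, beyond the figure, and uses a different time origin. This bears on time-averaged proteinuria and the slopes, not on the primary visits.

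**What to change.** Replace the two frequency sentences at the end of Section 4.4 with the visit months of Figures 2A and 2B, and state that all months are counted from randomisation. If the sponsor does want ACiGaN values at months 3, 5 and 7, those visits should be added to Figure 2A so that text and figure agree.

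In the same amendment, reconcile the primary time points: Section 6.4 has 6 months (ACiGaN) and 12 months (CHRONiGaN), while Section 4.4 has 4 and 8 months and 10 months. The sponsor should choose one set, use it throughout, and confirm that the schedule contains the chosen visit. The figures already include every candidate month (4, 6 and 8 in Figure 2A; 10 and 12 in Figure 2B), so they serve whichever choice is made.

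The cost is about one paragraph in Section 4.4 and a matching correction of the time points in Section 6.4 or 4.4. Adopting the figures as they stand adds no visits beyond them.
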